#### **6.10** Adherence Outcomes:

- 6.10.1 The primary outcome will be time to last use of a treatment element (lesson or tool), and will be tested between groups using traditional survival (Kaplan-Meier) methods, where the event of interest is last use from intervention start. Secondary analyses of the primary outcome would include Cox regression models that would adjust for potential effect modifiers or moderators such as gender, race, and age.
- **6.11** Patient Centered Outcomes:
- 6.11.1 Although power was presented for independent t-tests, primary analyses for patient centered outcomes (QIDS-C, MDD, and PHQ-9) will utilize generalized linear mixed (GLM) models (with link functions depending on the distribution of the outcome), that can examine patterns over the course of treatment and follow-up, and can account for missing data.(Gibbons et al., 1993)
- **6.12** Secondary Mediation Analyses:
- 6.12.1 Mediators will be entered into our models as time-varying covariates. We used the framework of Muller and colleagues(Muller, Judd, & Yzerbyt, 2005) to identify those variables, which mediate the effects of treatment on depression. Only if the 4 criteria specified by Muller are satisfied (treatment effect for depression, treatment effect for the mediator, effect of mediator on depression, and reduction of treatment effect when mediator is included), will we calculate the effect of mediation using MacKinnon and colleagues' product of coefficients method.(MacKinnon, Lockwood, Hoffman, West, & Sheets, 2002) Bias-corrected 95% confidence intervals for the mediated effect will be calculated using bootstrapping.(Shrout & Bolger, 2002)
- 6.12.2 Development of the recommendation engine algorithms will use machine learning and Baysean. statistical methods that will continuously learn that will continuously learn from user interactions with IntelliCare to provide intervention recommendations.
- **6.12.3** Exploration of moderating variables on outcomes, such as baseline demographics, baseline characteristics.
- 2.2.3 Explore, optimize, and validate coaching methods. This will include analyses of all data captured in the delivery of coaching, including the timing and content of messages and phone calls, and coach records related to participant encounters.

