#### 2 STUDY OBJECTIVES

- **2.1** Primary Objectives
- 2.1.1 Develop IntelliCare and optimize its functionality through laboratory and field usability testing.
- 2.1.2 Develop the machine learning models and algorithms that will continuously learn from user interactions with IntelliCare to provide intervention recommendations and motivational messaging.
- 2.1.3 Conduct a randomized controlled trial (RCT) comparing 8 weeks of IntelliCare with the machine learning component to 8 weeks of IntelliCare without the machine learning component for the treatment of depression and anxiety. Participants will be evaluated at baseline, week 4, week 8, and at 3- and 6-month post-treatment follow-ups. It is hypothesized that 1) IntelliCare with the recommendations, in contrast to IntelliCare without the recommendations, will produce greater adherence and greater reductions in depressive and anxiety symptoms and 2) IntelliCare with coaching will produce greater greater adherence and greater reductions in depressive and anxiety symptoms. The primary patient centered outcome will be depression/anxiety severity.
- 2.2 Secondary Objectives.
- 2.2.1 Exploration of the mediating effects of adherence markers (e.g. time in treatment, app launches, etc.) coaching variables (e.g. message frequency, timing, etc.), and psychological variables (e.g. change in self-report measures) on depression and anxiety outcomes.
- **2.2.2** Exploration of moderating variables on outcomes, such as baseline demographics, baseline characteristics.
- 2.2.3 Explore, optimize, and validate coaching methods.

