# PHASE 3 RANDOMIZED CONTROLLED TRIAL

- 4.1.4 Phase III Randomized Controlled Trial. For the RCT, 300 participants meeting entry criteria will be enrolled over 13 months (approximately 23 per month). Participants will be randomized using a factorial design with the following factors:
- **4.1.4.1** Factor 1. Hub App with intelligent recommender system/Hub app without intelligent recommender system: This factor is consistent with Objective 2.1.3 on pg. 4
- **4.1.4.2** Factor 2. Coaching/No Coaching: This factor would allow us to examine and control for the effect of coaching.
- **4.1.5** *Phase III Enrollment.* Participants in the RCT will be enrolled remotely to avoid excluding individuals with access barriers who are among those who would be likely end users. Screening will be conducted in 3 stages.
- 4.1.5.1 Screening Stage 1 (pre-consent): Interested parties will complete a brief web screen to determine whether there is any reasonable expectation that they might be eligible (data from the brief screen will be included in the study dataset). If they are clearly not eligible they will be informed of this and thanked. If they appear to be eligible a research assistant will follow-up by phone to clarify responses from the web screen and ask additional phone screening questions. If the participant passes the stage 1 phone screen s/he will be invited to initiate the online consent process and proceed to screening stage 2 described below.

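### Coaching is a randomised factor with its own hypothesis, but the RCT analysis does not state the coaching contrast or how coaching enters the tests

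*Combined protocol and SAP*

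**What the plan says.** Section 2.1.3, under Primary Objectives, describes the RCT as "comparing 8 weeks of IntelliCare with the machine learning component to 8 weeks of IntelliCare without the machine learning component". It then gives two numbered hypotheses. The first concerns the recommender. The second is that "IntelliCare with coaching will produce greater greater adherence and greater reductions in depressive and anxiety symptoms".

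Section 4.1.4 specifies a factorial design. Of Factor 1 (hub with or without recommender), 4.1.4.1 says "This factor is consistent with Objective 2.1.3 on pg. 4". Of Factor 2 (coaching or none), 4.1.4.2 says "This factor would allow us to examine and control for the effect of coaching". Section 4.1.6 allocates 75 participants to each of four groups, so each factor margin is 150 vs 150.

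The RCT part of section 6 then says:
- 6.9.2: 135 per arm, 270 in total, gives 80% power by log-rank test. The factorial structure is not mentioned.
- 6.10.1: time to last use "will be tested between groups using traditional survival (Kaplan-Meier) methods". Secondary Cox models would "adjust for potential effect modifiers or moderators such as gender, race, and age".
- 6.11.1: the patient-centred outcomes "will utilize generalized linear mixed (GLM) models (with link functions depending on the distribution of the outcome". No factor, contrast or interaction is listed.
- 6.12, item numbered 2.2.3, is the only RCT analysis text in section 6 that mentions coaching: "This will include analyses of all data captured in the delivery of coaching".

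**The concern.** The protocol randomises coaching in order to estimate its effect and to control for it, but section 6 contains no sentence that does either explicitly. The word groups in 6.10.1 has three possible meanings, and 4.1.6 uses it for the four cells. The sentence is also identical to 6.6.1, which covers the single-arm field trial, where there are no groups to compare. It therefore does not look as though it was written with the factorial in mind.

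Two things are at stake. First, a hypothesis listed under the primary objectives has no stated contrast, adjustment or treatment of interaction, so all three could be chosen after the results are known. Second, the recommender test loses some power if coaching works and is left out, and loses more if the sentence is carried out literally as a four-group test.

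**Working it through.** **The plan's own figure.** Inputs from 6.9.2: medians 7 and 10 weeks, 135 per arm, 5% type I error (taken as two-sided), accrual A = 54 weeks, then F = 12 weeks. With exponential times, λ₁ = ln2/7 = 0.0990 and λ₂ = ln2/10 = 0.0693, so HR = 0.70. The probability of an event is 1 − (e^(−λF) − e^(−λ(A+F)))/(λA), which gives 0.943 and 0.886.
- Expected events: 247.0 at N=270, and 274.5 at N=300.
- Schoenfeld power at 247 events: Φ(√247/2 × |ln 0.70| − 1.96) = Φ(2.803 − 1.960) = 80%.

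The stated 80% reproduces as a two-arm, 1-df calculation, which is one factor margin. The same formula at 274.5 events gives 84%.

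**Literal four-group test (3 df), hub-only HR 0.70.** The non-centrality is events × 0.25 × (ln 0.70)².
- 247 events: 7.86, power about 65%.
- 274.5 events: 8.73, power about 70%.

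**Hub A vs B, with and without stratifying by coaching.** Simulation with 4 × 75 participants, exponential times, hub HR 0.70, no interaction, 54+12 weeks and 20,000 replicates (Monte Carlo SE at most 0.35 points). The version B median is 7 weeks over both coaching levels. The documents give no coaching HR, so the values below are assumptions.

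| Coaching HR | Unstratified | Stratified | Difference (points) |
|---|---|---|---|
| 1.0 | 83.4% | 82.9% | −0.5 |
| 0.7 | 81.5% | 82.4% | +0.9 |
| 0.5 | 76.9% | 82.1% | +5.2 |

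Setting the 7-week median in the uncoached version B cell instead (4,000 replicates) gives 84/83%, 82/83% and 76/80%. If follow-up were censored at week 8 (an assumption; 4.1.6 says app data continue to be collected), the pairs at coaching HR 0.7 and 0.5 are 57.7/58.4% and 55.0/57.6%. The censoring rule is a separate question and adds no weight here.

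With hub HR 1.0, the simulated type I error is 4.2-5.4% for both tests in every scenario. On 400,000 simulated patients (54+12 weeks), the hub HR with coaching left out of the Cox model is 0.704 (coaching HR 0.7) or 0.719 (coaching HR 0.5), against 0.70 with it included.

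**Coaching margin, stratified by hub.** At coaching HR 0.70 without interaction, simulated power is about 83%. This depends on the second component working as well on top of the first as it does alone. A check with 274.5 events, where √274.5/2 = 8.284, uses the mean log HR over the two strata:
- Second component adds only HR 0.82 (0.70/0.85): mean log HR −0.275, Φ(8.284 × 0.275 − 1.96) = about 63%. Simulations give about 61-63%.
- Second component adds nothing: mean log HR −0.178, Φ(8.284 × 0.178 − 1.96) = about 31%. Simulations give about 30-32%.

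These margin figures apply to the hub test as well. Power for the interaction itself is low: Φ(√(d/16) × |ln 0.70| − 1.96) = 29% at d = 247 and 31% at d = 274.5, for an assumed ratio of HRs of 0.70.

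**The case against.** The strongest reply is that both margin tests are already implied. Section 2.1.3 gives the direction and outcomes of the coaching hypothesis, 4.1.4.2 names the contrast and its purpose, and 6.10.1 and 6.11.1 supply the methods. This stands as far as inference goes, and it rules out several stronger readings.

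- A reader might infer that the plan does not control for coaching. The documents do not support that. The Cox list gives examples only, 6.11.1 names no terms at all (not even the recommender), and the groups are undefined. Coaching is not stated, but it is not excluded.
- A reader might infer that hypothesis 2 has no test. A margin test can be inferred in the same way as for the hub.
- A reader might infer that the coaching item in 6.12 could not contain a coached-vs-uncoached comparison. Its list of analyses is not exhaustive. It is fair to say only that it states no such comparison.

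It is also fair that the measured power loss is small at a moderate coaching effect, and that the 5-point figure needs an assumed coaching HR of 0.5. What remains is that an inferable test is not a pre-specified one. The choice among a margin test, a four-cell test and a modelled effect is left open for a hypothesis under the primary objectives.

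**Conclusion.** The point holds as an omission of specification. The factorial design and its two hypotheses are not carried into 6.10.1 or 6.11.1, and the coaching contrast and its adjustment can be inferred but are not stated.

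It should not be read as a finding of bias. Coaching is randomised and balanced by design, no type I inflation appears for hub A vs B, and 135 per arm is a valid size for one factor margin.

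The main cost is freedom of choice after the data are seen, which the power figures do not measure. The measurable cost to the hub test is about 1 point of power at coaching HR 0.7 and about 5 at 0.5 (N=300, hub HR 0.70, 54+12 weeks, no interaction, coaching HRs assumed). Power falls to about 65-70% if the sentence is taken as a 3-df test. The 83% for coaching holds only without interaction.

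**What to change.** - **6.10.1:** define two 1-df main-effect tests: hub A vs B (groups 1+2 vs 3+4) and coaching vs no coaching (groups 1+3 vs 2+4). Adjust each for the other randomised factor by a stratified log-rank test. A Cox model with both factors is equally acceptable.
- **Secondary Cox models:** include both factors.
- **6.11.1:** include both factors and their interactions with time in the mixed models.
- **Interaction:** report hub-by-coaching as an estimate with its confidence interval.
- **6.9.2:** say that 135 per arm refers to a single factor margin and assumes no interaction.
- **For the sponsor to state:** which hypothesis is primary, since both stand under Primary Objectives, and whether the two share alpha. Each at its own 5% is defensible in a factorial. For time to last use alone, two independent tests give a family-wise error of 1 − 0.95² = 9.75%.

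The cost is SAP wording. Both factors are already randomised and recorded, and no extra participants or data are needed. The downside is about half a point of hub power (83.4% to 82.9%) if coaching has no effect.

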# STUDY SUMMARY

Full Protocol Title	Artificial Intelligence in a Mobile Intervention for Depression and Anxiety (AIM)
Short Title	IntelliCare Study
Protocol Number	IRB# STU00074405
Methodology	Phase 1: Intervention development and user testing, Phase II: Field Trial, Phase III: Randomized Controlled Trial.
Study Duration	5 years
Study Center(s)	Single-center
Objectives	The primary aim of this study is to develop and evaluate the use of state of the art machine learning approaches within a mobile phone intervention application for the treatment of symptoms of depression and anxiety.
Number of Subjects	Up to 1,250 participants
Diagnosis and Main Inclusion Criteria	Clinically significant symptoms of depression and/or anxiety.
Study Product(s), Dose, Route, Regimen	IntelliCare (mobile phone based mental health intervention)
Statistical Methodology	The primary outcome will be time to last use of a treatment element (lesson or tool), and will be tested between groups using traditional survival (Kaplan-Meier) methods, where the event of interest is last use from intervention start.

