- **4.1.5.4** Study Enrollment: A research study assistant will work with participants to download the IntelliCare apps from the Google Play store, and if assigned to work with a coach, schedule the coach orientation call.
- **4.1.6** *Phase III Treatment Plan.* The IntelliCare intervention will be comprised of a combination of 3 components: (1) IntelliCare Treatment Apps, (2) IntelliCare Hub App, (3) and Coaching. A brief description of each component appears below.
  - 1. IntelliCare Treatment apps: There are 13 IntelliCare treatment apps. Each app instantiates a single behavioral strategy (e.g. scheduling positive behaviors, thought restructuring, goal setting, etc.), and takes only a few seconds to use. The apps address specific treatment goals, and may include didactic content as well as interactional components (e.g. activity scheduling/monitoring, thought records, etc.) that support behavior change. All participants will download the apps onto their own phones and use them daily during the 8 week intervention period.
  - 2. IntelliCare Hub app: The "Hub" app integrates the treatment apps and organizes the user's experience. We will be testing two different versions of the hub app; one with an intelligent recommender system (version A) and one without (version B). The recommender system in version A will use machine learning, which can learn from a patient's interactions with the intervention, to deliver and adapt treatment to the needs and preferences of the participant.
  - 3. Coaching: BA level coaches (supervised by a licensed psychologist), may support participants throughout the 8 week intervention period. We have developed a low-intensity coaching model that relies primarily on brief text messaging to promote engagement, along with one engagement orientation call at the beginning of treatment, and the option of a second call if needed.

While **all** participants will have access to the treatment apps during the 8-week intervention period, the version of the Hub app and the inclusion of coaching will vary for each participant according to random assignment to one of 4 groups:

```
Group 1 (n=75): Hub App Version A + Treatment Apps + Coaching
```

Group 2 (n=75): Hub App Version A + Treatment Apps + Independent Use (no coaching)

Group 3 (n=75): Hub App Version B + Treatment Apps + Coaching

Group 4 (n=75): Hub App Version B + Treatment Apps + Independent Use (no coaching)

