#### 4.3 Data

- **4.3.1.1.1** *Adherence:* The primary adherence outcome will be length of time from initiating treatment to last use of treatment elements. We will also explore the motivational system by examining the number of motivational messages delivered, number viewed and the ratio of viewed/delivered by treatment arm. More specifically:
- **4.3.1.1.1.1** Messages include text and email messages between participants and study staff for the purposes of coaching and participant management.
- **4.3.1.1.2** App use includes the number, timing, and duration, application launches and launches of specific pages within the app.

- **4.3.1.1.2** *Depression:* Primary patient centered outcomes will use continuous measures of depression and anxiety.
- **4.3.1.1.2.1** *PHQ-9* will be used to evaluate self-reported depression. GAD-7 will be used to evaluate self-reported anxiety.
- **4.3.1.1.3** *Secondary Outcome Measures* will include the following (for a full list of self-report measures see Measures Appendix):
- **4.3.1.1.3.1** *Satisfaction*, measured using the USE questionnaire, which was designed to measure satisfaction, usefulness, ease of use, and ease of learning.

*Moderators and mediators* will include the measures provided prior to initiating treatment the Mini International Neuropsychiatric Interview, the SCT Motivation assessment, Behavioral Activation, wellbeing and quality of life, Coping, and

**4.3.1.1.3.2** Audiofiles include audio recordings of coaching and assessments. Audio files may be transcribed by one or more of the following NU transcription vendors:

GMR Transcription https://www.gmrtranscription.com/

Wordsworth https://wordsworthcoop.com

Files may be shared via secure access to FSM servers or through vendors' proprietary web-based applications for secure file management.

- **4.3.1.1.4** Coach generated notes on participant encounters.
- 4.4 Removal of Subjects from Study

Patients can be taken off the study treatment and/or study at any time at their own request, or they may be withdrawn at the discretion of the investigator for safety, behavioral or administrative reasons. The reason(s) for discontinuation will be documented and may include:

- 4.4.1 Patient voluntarily withdraws from treatment (follow-up permitted);
- 4.4.2 Patient withdraws consent (termination of treatment and follow-up);
- 4.4.3 Patient is unable to comply with protocol requirements; (termination of treatment and follow-up);

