- 6.9.2 Preliminary data indicates that approximately 50% of patients stop participating in BITs (which we define here as "drop out") by week 7 (see Sec. D.1.1). A sample size of 135/arm (total sample of 270) will provide 80% power to detect a difference in median drop out time from 7 to 10 weeks. We estimate from existing data (Sec D.1.1) that a 3 week increase would result in an 11% improvement in depression severity (ES=0.30). Additionally, this sample provides 80% power to detect an increase in continued participation from 50% to 61.6% at week 7. Both analyses are based on a log-rank test at a type 1 error rate of 5%, with accrual of 54 weeks and 12 weeks of intervention. Power for continuous patient

centered outcomes were based on independent t-tests, and would have 80% power to detect effect sizes of 0.34. Power calculations were performed using Pass 2008.(Hintze, 2008)

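### Section 6.10.1 makes last use the primary adherence event without an end of observation, inactivity gap, censoring rule or never-user rule, and its power input of 12 weeks conflicts with an 8-week intervention

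*Combined protocol and SAP*

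**What the plan says.** Section 6.10.1 defines the RCT primary outcome as time to last use of a treatment element, tested between groups with Kaplan-Meier methods, "where the event of interest is last use from intervention start". The Study Summary repeats this. Section 4.3.1.1.1 gives it as "length of time from initiating treatment to last use of treatment elements". None of these places states an end of observation, an inactivity gap, a censoring rule or a rule for people who never open an element.

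Section 6.9.2 rests on preliminary data in which "approximately 50% of patients stop participating in BITs" by week 7. It claims 80% power with 135 per arm to detect a change in median from 7 to 10 weeks, using a log-rank test "with accrual of 54 weeks and 12 weeks of intervention". Objective 2.1.3 describes a trial "comparing 8 weeks of IntelliCare with the machine learning component to 8 weeks of IntelliCare without the machine learning component", and 4.1.6 asks participants to download the apps and "use them daily during the 8 week intervention period". After week 8 participants may keep using the apps, logging goes on with no stated end, and groups 1 and 3 lose their coach (4.1.6). Symptom assessments run to 6 months after treatment (4.1.6.1). Planned enrolment is 300.

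**The concern.** Everyone who opens a treatment element has a last use, so the event as worded happens to every user. It becomes analysable only once someone decides when observation ends and what silence counts as stopping. At least three horizons fit the text: 8 weeks (treatment), about 34 weeks (8 plus the 6-month follow-up), and 12 to 66 weeks (the follow-up implied by 6.9.2).

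The choice affects two things. The first is the number of events, and so the power. The second is what is measured. With a cut-off at week 8 and no gap rule, a person who is still active gets an event date set by how often they use the apps. With a long horizon, the coaching contrast also covers the period after coaches are withdrawn. As written, the choice could be made after the data are seen.

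Time zero is also unsettled. Sections 4.3.1.1.1 and 6.10.1 use different words for the start, and someone who never starts has no initiation date.

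**Working it through.** **Inputs.** From 6.9.2: medians 7 and 10 weeks, 270 people allocated 1:1, log-rank at 5%, accrual a = 54 weeks, further follow-up f = 12 weeks. From 4.1.4: 300 planned. Assumptions: exponential stopping and a two-sided test (a one-sided test gives 87.7% and does not match the plan).

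**Hazard ratio.** 7/10 = 0.70. The plan's second statement of the effect agrees: ln(0.616)/ln(0.5) = 0.699.

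**Events needed (Schoenfeld).** 4(1.960 + 0.842)²/(ln 0.70)² = 247.

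**Reproducing 80%.** With hazard λ = ln 2/median and uniform accrual, P(event) = 1 − [exp(−λf) − exp(−λ(a+f))]/(λa).
- Median 7: 1 − (0.3048 − 0.0015)/5.347 = 0.943.
- Median 10: 1 − (0.4353 − 0.0103)/3.743 = 0.886.
- Mean 0.915, and 270 × 0.915 = 247 events.
- Power = Φ(√247 × 0.3567/2 − 1.960) = Φ(0.843) = 80.0%.

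The plan's figure is reproduced, with each person observed to one calendar end, 12 to 66 weeks after starting.

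**Same effect, other horizons.** For a fixed horizon h, P(event) = 1 − exp(−λh). At h = 8 this is 0.547 and 0.426, mean 0.486.

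| Observation per person | Events of 270 | Power, 270 | Power, 300 |
|---|---|---|---|
| 12-66 weeks | 247 | 80.0% | 84.0% |
| 8-62 weeks | 238 | 78.6% | 82.7% |
| Fixed 34 weeks | 253 | 80.9% | 84.8% |
| Fixed 12 weeks | 170 | 64.3% | 68.9% |
| Fixed 8 weeks | 131 | 53.3% | 57.7% |

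The 12-versus-8 conflict alone costs 1.4 points. Ending observation with treatment costs about 27. At a fixed 8 weeks, 247/0.4864 gives about 508 people for 80% power.

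**Effect of use frequency.** On the plan's medians, 2^(−8/7) = 45% and 2^(−8/10) = 57% are still active at week 8. If all were given an event exactly at week 8, the log-rank test would be the same as if they were censored there. The difficulty is that recorded last uses scatter over the days before the cut-off, and more widely when use is sparser. In simulations of 150 versus 150 with identical stopping (median 7 weeks) and assumed shares of days with use, the test rejected as follows:

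| Rule | 80% v 90% | 70% v 90% | 1/3 v 1/2 | 1/4 v 1/2 |
|---|---|---|---|---|
| 8 weeks, every last use an event | 9% | 21% | 31% | 67% |
| 34 weeks, every last use an event | 5% | 5% | 6% | 6% |
| Day-42 cut-off, days 43-56 use-free | 6% | 5% | 5% | 7% |

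At once versus twice a week the three rules give 69%, 7% and 22%.

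**Two workable rules, 300 people, 7 v 10 weeks.**
- Day-42 cut-off: P(event) is 0.448 and 0.340, mean 0.394, giving 118 events and 49.2% power (simulated 49%).
- Week-26 cut-off with weeks 27-34 as the check: P(event) is 0.924 and 0.835, mean 0.879, giving 264 events and Φ(0.937) = 82.6% (simulated 82%). Rejection under equal stopping was 5-7%, including once versus twice a week.

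**After coaching ends.** Suppose 30% of active coached users stop at week 8 (an assumption). Over 12-66 weeks the test then goes against coaching in 27% of trials with identical in-treatment stopping. At 10% and 50% the figures are 7% and 63%.

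**The case against.** The strongest reply is that the power paragraph does state its follow-up. A log-rank calculation with accrual and follow-up implies censoring at a data cut-off, its inputs return 80.0%, and 4.1.6 keeps the logs running after week 8, so long observation is possible. This stands. A reader might infer that the 80% is a miscalculation, or that the trial really has 53% power. The documents support neither: 53% follows only if observation stops at week 8, which they do not say. What is missing is any link from the follow-up in 6.9.2 to the analysis in 6.10.1.

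A reader might also infer a false-positive rate of 31-67%. That needs the least supported reading (week-8 end, nobody censored) together with use on a quarter to a half of days, differing by arm, in a trial that asks for daily use. Near daily use the figure is about 9%, and at 34 weeks 5-7%. More frequent use is also a real aspect of adherence; it misleads only if the outcome is meant to be stopping.

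Section 6.9.2 cites a Sec. D.1.1 that is not among the documents and may define drop-out. Section 6.10.1 does not refer to it, so it cannot be relied on to fill the gap.

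**Conclusion.** The concern holds in this form: the primary adherence event is not operationally defined, and the intervention length behind its power conflicts with the rest of the protocol. It must be fixed, because the open choices move power between about 53% and 81% with 270 people and change the question being tested.

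The power figures rest on the plan's medians and exponential stopping. The rejection rates rest on assumed use frequencies and week-8 stopping shares that have no source in the documents; they show direction and range and do not predict this trial.

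Two further inferences should be avoided. Stopping after coaches are withdrawn is a real difference in time to last use, not a type I error, and it does not bias the recommender contrast, where coaching is balanced. Nor do the documents show that an in-treatment rule is the only right one. The day-42 example ends before the plan's own week-7 target, whereas a long horizon answers a broader question. Long horizons are not always the more powerful choice either: if the benefit exists only in weeks 0-8, power with 270 people is about 33% over 12-66 weeks, against 53% at a fixed 8 weeks. The PHQ-9 and GAD-7 analyses are unaffected.

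**What to change.** Before unblinding, state in 6.10.1:

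1. Time zero, as one date that exists for every randomised participant, including those who never open an element.
2. One observation horizon, the same for both factors.
3. That a last use is an event only if a stated use-free period follows it and is fully observed; people still using are censored at the cut-off.
4. That never-users count as events at time 0.
5. That people whose data collection ends early, for example at consent withdrawal (4.4.2), are censored then.

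Choose one rule as primary and report the other as a sensitivity analysis. The in-treatment example (day-42 cut-off, days 43-56 as the check) has about 49% power with 300 people. The long-horizon example (week-26 cut-off, weeks 27-34 as the check) has about 82% and should be labelled as including the period after coaching ends. Reconcile the 12 weeks in 6.9.2 with the 8 weeks in 2.1.3 and 4.1.6, and restate power for the chosen event and horizon.

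The cost is SAP wording and a few lines of code; the use logs are already collected. The in-treatment rule lowers the stated power (to 44% or 40% if 5% or 10% in both groups never open an element), leaves stopping in weeks 7-8 uncounted, and still rejects too often with very sparse use. The long-horizon rule needs logs complete to week 34, and its power falls to 69% if 30% of active users in both arms stop at week 8 (an assumption).
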